5 RANDOMIZATION

Pain scores reported by subjects during the Screening Period will be evaluated by the interactive response technology (IRT) system for raw score and for variability among scores after transmission of pain scores from the handheld devices to determine randomization eligibility. Subjects whose mean of the daily average pain intensity score during the preceding 7 days within the protocol-defined algorithm and whose compliance with daily diary completion is found to be adequate will be eligible for randomization. The absolute pain scores and variability among scores, as well as the actual percentage required for diary compliance, will be masked to investigators and subjects. Subject eligibility for randomization into the study based on these variables will be communicated to the investigator via the IRT system. The IRT system notified the site if the subject is “Eligible” or “Not eligible.” No other information will be provided.

6 PLANNED ANALYSES

The final Clinical Study Report (CSR) may contain additional tables or statistical tests if warranted by the data obtained. The justification for any such additional analyses will be fully documented in the final CSR.

6.1 Analysis Population

Subjects excluded from the analysis populations and the reason for their exclusion will be listed in [Appendix 16.2](#).

6.1.1 Screened Population

The Screened Population includes all subjects who are screened.

6.1.2 Randomized Population

The Randomized Population includes all subjects who are randomized.

6.1.3 Safety Population

The Safety Population includes all subjects who received at least one dose of study drug. For safety analyses, subjects will be grouped based upon the treatment received. In the event that a subject receives both treatments (NYX-2925 and placebo), the subject will be grouped under NYX-2925.

6.1.4 Modified Intent-to-Treat Population

The Modified Intent-to-Treat (mITT) Population includes all subjects in the Safety Population with at least one post-baseline assessment of the pain intensity NRS. Efficacy analyses for the mITT Population will have subjects grouped based on their planned treatment. All efficacy analyses will be performed on the mITT Population.

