- Change from baseline to Week 12 in the Patient Reported Outcomes Measurement Information System – Fibromyalgia (PROMIS_{FM}) sleep disturbance score
- Change from baseline to Week 12 in the Patient Reported Outcomes Measurement Information System – Fibromyalgia (PROMIS_{FM}) fatigue profile score
- Change from baseline to Week 12 in the Patient Reported Outcomes Measurement Information System – Fibromyalgia (PROMIS_{FM}) physical function score
- Cumulative response (percent reduction from baseline) in the weekly mean NRS average pain intensity at Week 12
- Use of rescue medication, including the proportion of subjects using rescue medication, the frequency and amount used

- Change from baseline in the weekly mean of the daily Numerical Rating Scale (NRS) at each week from Week 1 through Week 12

Other Efficacy Endpoints:**Safety Endpoints:**

- Adverse events and serious adverse events
- Discontinuations due to adverse events
- S-STS

Sample Size:

The planned sample size is 300 randomized subjects. This will provide approximately 80% power for statistical testing with an overall Type I error rate of 0.05.

Statistical methods:

Safety analyses will be based on the Safety Population, defined as all subjects who receive at least one (1) dose of study drug. Efficacy analyses will be based on the modified Intent-to-Treat Population, defined as all subjects in the Safety Population with at least one (1) postbaseline assessment of the weekly mean of pain intensity NRS.

Change from baseline will be assessed for treatment group differences with a mixed model repeated measures (MMRM) with factors for study site, treatment, week, and the treatment-by-week interaction, with baseline value as a covariate.

As a sensitivity analysis, an analysis of covariance (ANCOVA) with fixed factors for study site and treatment, with baseline value as a covariate will be used.

Change in the weekly mean of the daily NRS scores assessing average pain intensity in the past 24 hours from baseline will be assessed for treatment group differences using an MMRM and ANCOVA analogous to the primary efficacy analysis described above. Change from baseline for the FIQR, [REDACTED] DSIS and PROMIS_{FM} (sleep disturbance, fatigue profile and physical function) will be analyzed similarly. The PGI-C will be summarized at each evaluation.

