12.4. Analysis Populations

Safety analyses will be based on the Safety Population, defined as all subjects who receive at least one dose of study drug.

Efficacy analyses will be based on the modified Intent-to-Treat Population, defined as all subjects in the Safety Population with at least one postbaseline assessment of the pain intensity NRS.

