4 SAMPLE SIZE

The planned sample size is a total of 300 randomized subjects with 100 subjects per treatment group. Efficacy analyses will include all subjects who receive at least one dose of study drug and who have at least one post baseline assessment. It is expected that approximately 15% of subjects will be excluded from the efficacy population. A total of 85 subjects per treatment arm will provide approximately 88% power to detect a difference in means of 0.73 for NYX-2925 50 mg or 100 mg versus Placebo group assuming that the common standard deviation is 1.7 without correcting for multiple testing, using one-sided statistical testing with an overall Type I error rate of 0.05.

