2.2.2 New Text

The primary efficacy analysis will evaluate the treatment-policy estimand to estimate the improvement (reduction) from Baseline in the weekly mean of the daily NRS score in subjects in the modified ITT population not discontinuing treatment early due to an AE or lack of efficacy through Week 12.

The following four attributes describe the estimand that will be used to define the treatment effect of interest for the primary efficacy analysis:

- Population = Subjects meeting the protocol-specified inclusion/exclusion criteria, who received at least one dose of study drug and who have at least one post-baseline assessment of the pain intensity NRS.
- Subject-level outcome = Change from baseline in the weekly mean of the daily NRS score assessing average pain intensity in the past 24 hours
- Intercurrent event handling = An intercurrent event is defined as discontinuation of study drug due to an AE or lack of efficacy prior to Week 12. For primary efficacy analysis purposes, baseline Observation Carried Forward (BLOCF) imputation will be used to impute data for visits after a patient has discontinued randomized treatment due to either of these reasons (even if data is present).
- Population-level summary measure = Difference in least squares (LS) mean change from baseline in the weekly mean of the daily NRS score at Week 12, comparing each dose of NYX-2925 to placebo.

Any missing data at Week 12 that are not preceded by an intercurrent event (i.e., discontinuation of study drug due to AE or lack of efficacy) will remain as missing.

2.3 Change 3

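### The efficacy population drops dosed subjects who stop for an adverse event or lack of efficacy before any diary entry, although the primary rule could score them as no change from baseline alone

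*SAP*

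**What the plan says.** SAP 6.1.3 sets the Safety Population at one dose or more. SAP 6.1.4 then defines the mITT set, which "includes all subjects in the Safety Population with at least one post-baseline assessment of the pain intensity NRS", and adds: "All efficacy analyses will be performed on the mITT Population". Protocol 12.4 has the same condition ("subjects in the Safety Population with at least one postbaseline assessment of the pain intensity NRS"). The protocol synopsis words it differently, on the weekly mean: "at least one (1) postbaseline assessment of the weekly mean of pain intensity NRS". The population attribute of the primary estimand repeats the post-baseline condition (Protocol 12.6.1, SAP 6.11.1.1, addendum 2.2.2).

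The intercurrent event is stopping study drug for an adverse event or lack of efficacy before Week 12, with no minimum time on treatment. The plan handles it by carrying the baseline value forward (BLOCF); this "imputation will be used to impute data for visits after a patient has discontinued randomized treatment due to either of these reasons". It overrides any scores recorded after the stop. Addendum 2.3.2 confirms the rule for the primary model. The only input it needs is the baseline mean NRS, which requires at least 5 of the 7 pre-dose days (SAP 6.2.17.1).

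On numbers excluded, SAP 4 says: "It is expected that approximately 15% of subjects will be excluded from the efficacy population". It does not split this by reason.

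**The concern.** The handling rule treats an early stop for an adverse event or lack of efficacy as a failure and scores it as no improvement. The earliest such stop, after the first dose and before the first diary entry, is as clear a failure as any, yet the population definition removes it. Whether a failure is counted then turns on whether one diary entry was made, which happens after randomisation and may be linked to tolerability. At stake is whether the Week 12 comparison covers the failures that the rule was written to capture, and whether the arms compared are still the arms as randomised and dosed.

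**Working it through.** **Inputs from SAP 4.** 100 randomised and 85 analysed per arm, difference 0.73, SD 1.7, one-sided alpha 0.05, stated power about 88%.

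**Reproducing the plan's figure.** 100 x (1 - 0.15) = 85. The standard error of the difference is 1.7 x sqrt(2/85) = 0.261, and 0.73/0.261 = 2.80. Power is Phi(2.80 - 1.645) = 0.876, which agrees with 88%. The 15% exclusion is therefore built into the sample size.

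**Tracing three dosed subjects with a baseline mean through the rules.**

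- Subject A stops for an adverse event on Day 1 with no diary entry. BLOCF could give change 0 at Weeks 1 to 12. The mITT definition excludes the subject.
- Subject B stops for the same reason after one Day 1 entry. That entry falls in Week 1 (SAP 6.2.17.2, last diary on Day 1 to Day 10) and no minimum number of post-baseline days is set. The subject is in mITT and is scored 0 at later weeks, including Week 12.
- Subject C stops for another reason with no entry. The subject is excluded, but all twelve weeks would have stayed missing anyway, so the mixed model would have gained nothing.

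In the primary model the post-baseline condition therefore matters only for subjects like A.

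**Does any other analysis recover A?** The pattern-mixture and tipping-point analyses are on mITT; the addendum (2.4.2, 2.5.2) extends both to data after an intercurrent event but leaves the population unchanged. The ANCOVA and pooled analyses are on mITT and, by addendum 2.6.2 and 2.7.2, use no imputation. None recovers A.

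**Size.** The documents give neither the number of such subjects nor the arm means. Assume mean changes of -2.2 (active) and -1.5 (placebo) in the analysed subjects, a gap of 0.70. Let pA and pP be the shares of each arm, after restoration, that are excluded stops with change 0.

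Difference on mITT = 2.2 - 1.5. Difference with them restored = (1 - pA) x 2.2 - (1 - pP) x 1.5. The shift due to exclusion is therefore 2.2 x pA - 1.5 x pP, positive when mITT favours the drug.

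- 1% active, 0% placebo: 0.022 - 0 = 0.022 (3% of 0.73, and under a tenth of the standard error of 0.261)
- 1% active, 1% placebo: 0.022 - 0.015 = 0.007
- 1% active, 2% placebo: 0.022 - 0.030 = -0.008

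Under these means the sign changes where pP = (2.2/1.5) x pA, about 1.5 times pA. If the two means are equal, the sign depends only on which arm loses more.

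**Loose ceiling.** With equal numbers restored in each arm, 0.73 shrinks by the restored share. One per arm gives 0.73 x 85/86 = 0.72. If all 15 excluded per arm were such stops, it would be 0.73 x 85/100 = 0.62. Taking each arm as a mixture of zeros and the rest, with an assumed placebo mean change of -1.0 to -2.0, one-sided power is 87% in the first case and 79% to 85% in the second. The second is a bound, not an expectation.

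**The case against.** The strongest reply is that the affected group is nearly empty by design. The first dose is taken in clinic and the diary is completed that same bedtime (Protocol 10.2). Baseline ends at Day -1 (SAP 6.2.2), so one entry on the first evening qualifies, and every randomised subject has just passed a diary-compliance check. A stop for lack of efficacy before that evening is hardly plausible, so the point concerns adverse events almost entirely. This stands, and it is why the size is put at the low end.

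Second, the population condition is written into the estimand itself and agrees across the SAP and Protocol 12.4, so no passage contradicts another. This also stands. The point is about a choice of analysis set that weakens the plan's own rule.

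Third, exclusions and their reasons will be listed (SAP 6.1, listing 16.2.3.1). A listing shows who was left out, but it does not put them into any estimate.

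A reader might go further and infer that early adverse-event stops are commoner on active drug, so that the mITT set flatters NYX-2925. The documents do not support this. Protocol 6.3 reports no adverse-event difference from placebo across the dose range in the two earlier Phase 2 studies, and Protocol 4 describes few discontinuations for adverse events. If placebo loses sufficiently more, the bias runs the other way.

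**Conclusion.** The point holds as a design weakness that is cheap to remove. The analysis set selects on a post-randomisation event and so omits the earliest cases of the failure that the primary rule scores as 0, and no planned analysis covers them. The likely effect is small: about 0.02 NRS points at 1% active against none on placebo, and about -0.01 at 1% against 2%. Both figures rest on the assumed means of -2.2 and -1.5 and on assumed shares; the true counts are not in the documents.

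The 15% in SAP 4 should not be read as the share of such failures. It covers every reason for exclusion, including randomised subjects who were never dosed, a group that SAP 6.4 anticipates. It serves only as a loose ceiling.

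**What to change.** Define the efficacy population as all randomised subjects who took at least one dose and have a baseline mean NRS. The baseline condition must be stated, because the diary-compliance threshold for randomisation is masked and cannot be checked against the 5-of-7 rule. Apply the existing BLOCF rule, change 0 at Weeks 1 to 12, to those who stopped for an adverse event or lack of efficacy with no post-baseline NRS, and leave all others missing as planned. Amend the estimand's population attribute to match and keep the current mITT as a supportive set. Align the synopsis wording with Protocol 12.4 and SAP 6.1.4: a weekly mean and a single assessment coincide only while no minimum number of days is set for a weekly mean.

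The SAP addendum states that it was written after database lock and unblinding. For this trial, the analysis should therefore be added as a sensitivity analysis labelled post hoc, not substituted for the primary. Alongside it, tabulate dosed subjects without a post-baseline NRS by arm and stopping reason. If there are few or none, that table closes the question.

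The cost is a derivation change, one further model run and one table, with no new data. The estimate may come out slightly less favourable to the drug.

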6.2 Derived Data

This section describes the derivations required for statistical analysis. Unless otherwise stated, variables derived in the source data will not be re-calculated.

6.2.1 Race

Where more than one race category has been selected for a subject, these race categories will be combined into a single category labeled “Multiple Race” in the summary tables. The listings will reflect the original selected categories.

6.2.2 Baseline

Baseline is defined as the last non-missing value (either scheduled, unscheduled or repeat) before the subject receives the first dose of study drug.

For endpoints in which the weekly mean is being utilized, baseline is defined as the average of the available assessments on the last 7 days prior to the first dose of study drug (study days -7 to -1).

6.2.3 Duration / Study Day / Time

Study day will be calculated as the number of days from first dose of study drug.

- date of event – date of first dose of study drug + 1, for events on or after first dose
- date of event – date of first dose of study drug, for events before first dose

6.2.4 Conventions for Missing and Partial Dates

All rules explained below for partial/missing dates will be followed unless contradicted by any other data recorded on the electronic Case Report Form (eCRF).

All dates presented in the individual subject listings will be as recorded on the eCRF (i.e., not completed as per the below rules).

6.2.5 Missing/Partial Start/Stop Date of Adverse Events and Concomitant Medications

Missing and partial start and stop date will be imputed for analysis purposes for Adverse Events (including Medical History) and Concomitant Medications as follows.

Partial or missing stop date will be imputed as follows:

- If the stop date is completely missing and the event has resolved or the subject has stopped taking the concomitant medication, the stop date will be imputed as the date of the subject's last clinic visit in the study.
- If only the year is known, the stop date will be imputed as "31-Dec" of that year or as the date of the subject's last clinic visit in the study if in the same year.
- If the month and year are known, the stop date will be imputed as the last day of that month unless the stop date corresponds to the same month as the subject's last clinic visit in which case the date of subject's last clinic visit in the study will be used instead.

Missing start date will be imputed as follows:

- If the stop date occurs on or after the start of study drug or the event/concomitant medication is ongoing, the start date will be imputed as the date of the first dose of study drug.
- If the stop date occurs before the start of study drug, the start date of the event/concomitant medication will be imputed as the subject's screening date or the stop date of the event/concomitant medication whichever the earlier.

Partial start date (year present, but month and day missing)

- If the stop date occurs on or after the start of study drug or the event/concomitant medication is ongoing, and the year is the same as the year of first dosing the start date will be imputed as "01-Jan" of the same year or the date of the first dose of study drug whichever is latest. If the year is different from the year of first dosing "01-Jan" will be used.
- If the stop date occurs before the start of study drug or subject was not dosed, the start date of the event/concomitant medication will be imputed as the "01-Jan" of the same year.

Partial start date (month and year present, but day missing)

- If the stop date occurs on or after the start of study drug or the event/concomitant medication is ongoing, the start date will be imputed as the first day of the same month and year unless this partial start date is in same month as the first dose of study drug in which case the date of first dose of study drug will be used.

- If the stop date occurs before the start of study drug subject was not dosed, the start date will be imputed as the first day of the month and year of the partial stop date.

6.2.6 Missing Last Dates of Study Drug Dosing

If the date of last dose of study drug is completely missing, then the date of last dose of study drug will be taken for analysis purposes as the date when the subject would have run out of study drug assuming full compliance from the date the study drug was last dispensed, or the date of subject's last clinic visit in the study (if study drug is returned) or early withdrawal or death whichever the earlier.

If only the month and year of the last dose was recorded, then the date of last dosing will be taken for analysis purposes as the date the subject would have run out of study drug assuming full compliance from the date the study drug was last dispensed, the last day of the month of the recorded last dose or the date of subject's last clinic visit in the study (if study drug is returned) or early withdrawal or death whichever the earlier.

6.2.7 Exposure to Study Drug

Exposure to study drug (days) will be calculated as follows:

$$(Date \text{ of } last \text{ dose } of \text{ study } drug - Date \text{ of } first \text{ dose } of \text{ study } drug) + 1$$

The exposure calculation will not take into account breaks in therapy.

6.2.8 Treatment Compliance

Treatment compliance will be calculated per visit interval (Visit 2 to Visit 4, Visit 4 to Visit 5, and Visit 5 to Visit 6) as follows:

$$\frac{\text{Total number of capsules dispensed} - \text{Total number of capsules returned}}{(\text{Number of days within the visit interval})} \times 100$$

Total number of capsules dispensed will be obtained as below:

- Visit 2 to Visit 4: the total number of capsules dispensed at Visit 2
- Visit 4 to Visit 5: the total number of capsules dispensed at Visit 4
- Visit 5 to Visit 6: the total number of capsules dispensed at Visit 5

Total number of capsules returned will be obtained as below:

- Visit 2 to Visit 4: the total number of capsules returned at Visit 4
- Visit 4 to Visit 5: the total number of capsules returned at Visit 5
- Visit 5 to Visit 6: the total number of capsules returned at Visit 6

The number of days within the visit interval is obtained as follows:

- Visit 2 to Visit 4: (Date of Visit 4 – Date of first dose of study drug) + 1
- Visit 4 to Visit 5: (Date of Visit 5 – Date of Visit 4)
- Visit 5 to Visit 6: (Date of Visit 6 – Date of Visit 5)

6.2.9 Inexact Values

In the case where a variable is recorded as “ $> x$ ”, “ $\geq x$ ”, “ $< x$ ” or “ $\leq x$ ”, a value of x will be taken for analysis purposes.

6.2.10 Electrocardiogram (ECG) Data

For electrocardiogram (ECG) data recorded on continuous scales, if more than one value (for instance, triplicate recordings) is recorded at a time point (i.e., date), the mean value rounded to the integer will be presented. in the event that one reading is missing, the average of the available two readings will be used for the analysis. Furthermore, if only one reading is available, this reading will be used for the analysis.

For overall interpretation if more than one interpretation is recorded, the most severe (worst case) interpretation will be presented.

6.2.11 Early Withdrawal Assessments

For the analysis, assessments performed at early withdrawal visits for the subjects who discontinued will be mapped to the closest visit, using midpoints between visits to window the early withdrawal. If the early withdrawal assessment is mapped to a visit where a scheduled assessment is already present, the scheduled assessment will take precedence, and the early withdrawal assessment will be disregarded (and listed only).

Note that the windowing will be specific to the measure, per the below table. For example, PGI-C is collected at Weeks 4, 8, and 12 and thus the early withdrawal assessment for PGI-C would be windowed with Day 2 to Day 42 as Week 4, Day 43 to Day 70 as Week 8, and Day 71+ as Week 12.

Assessment(s)	Timing of Early Withdrawal Assessment	Mapped Visit
Physical Exam	Day 2+	Week 12
Vital signs, Laboratory samples, PGI-C, FIQR, PROMIS _{FM} , PROMIS, ECG	Day 2 to Day 42	Week 4
	Day 43 to Day 70	Week 8
	Day 71+	Week 12
Sheehan STS	Day 2 to Day 21	Week 2
	Day 22 to Day 42	Week 4
	Day 43 to Day 70	Week 8
	Day 71+	Week 12

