Study Period	Screening		Baseline		Treatment Period		
	Study Week	1 to 4 weeks ^a (-28 to -1)	Week 0 ^d (1 ±2)	Week 2 (14 ±2)	Week 4 (28 ±4)	Week 8 (56 ±4)	Week 12 ^b (84 ±4)
Study Visit	Visit 1	Visit 2	Visit 3 ^v	Visit 4	Visit 5	Visit 6	
Record average pain intensity ^m and rescue medication use over past 24 hours at bedtime for each day	X	X	X	X	X	X	X
Randomize eligible subjects		X					
Dispense study drug ^o		X					
Confirm subject takes first dose of study drug (in the clinic)		X					
Confirm study drug dosing each day via handheld device		X	X	X	X	X	X
Return study drug and assess compliance ^l			X	X	X	X	X
Misuse, Abuse, and Diversion Drug Event Reporting System [®] (MADDERS) ^s				X	X	X	X
Record Daily Sleep Interference Scale (DSIS) each morning ⁿ	X	X	X	X	X	X	X
Assess handheld diary compliance		X	X	X	X	X	X
MINI International Neuropsychiatric Interview (MINI)	X		X	X	X	X	X
Fibromyalgia Impact Questionnaire – Revised (FIQR)				X	X	X	X
Patient Reported Outcomes Measurement Information System – Fibromyalgia (PROMIS _{TM}) ^t			X	X	X	X	X
Patient Global Impression of Change (PGI-C) scale					X	X	X
Sheehan Suicidality Tracking Scale (S-STS)	X	X	X ^v	X	X	X	X
Concomitant medications ^q	X	X	X	X	X	X	X
Adverse events ^r	X	X	X	X	X	X	X
Safety follow-up calls							X ^y

^a Subjects will discontinue all concomitant analgesic medications taken for pain related to fibromyalgia. Duration of the period will depend upon the analgesic(s) being discontinued, not to exceed 4 weeks. Subjects not taking any concomitant analgesic medications at Visit 1 may directly begin Week -1 of the Screening Period.

^b ET=Early Termination. Subjects who prematurely discontinue randomized treatment will have Week 12 procedures performed. Diary completion ends the night before the Week 12 visit.

^c Informed consent includes an additional consent for inclusion in a secure, proprietary, research subject database to screen for protocol violators. The main informed consent document may be executed up to 30 days prior to the screening visit. The date the first screening related activity is completed will be considered the subject's screening date. If the subject does not complete the screening visit within 30 days of signing the informed consent document, the subject must be reconsented.

^d Verify subject still meets all inclusion criteria and does not meet any exclusion criteria.

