9.3.5. Clinical Laboratory Assessments

Blood samples for serum chemistry and hematology will be obtained after an eight-hour fast.

The study investigator should monitor subjects during the study for signs of hepatic abnormality potentially meeting the stopping criteria ([Section 11](#)).

The investigator will review clinical laboratory test results as they become available, for determination and documentation of clinical significance (if there are out of range values). The investigative site will contact the medical monitor for any liver function test results that potentially meet the stopping criteria. Possibly drug-related or clinically significant abnormal values of uncertain causality must be repeated. Persistent abnormal laboratory values should be followed at the investigator's discretion. Abnormal liver function tests (specified in [Section 11](#)) must be repeated within 48-72 hours.

Hematology assessments will include hemoglobin, hematocrit, red blood cell count, white blood cell count, differential (neutrophils, lymphocytes, monocytes, eosinophils, and basophils) and platelet count.

Chemistry assessments will include glucose, calcium, electrolytes (sodium, potassium, bicarbonate, chloride), phosphorus, blood urea nitrogen (BUN), creatinine, albumin, total protein, magnesium, alkaline phosphatase (ALP), aspartate aminotransferase (AST), alanine aminotransferase (ALT), lactate dehydrogenase, gamma-glutamyl transferase (GGT), albumin, total bilirubin, direct bilirubin, indirect bilirubin, uric acid, and C-reactive protein (CRP). A thyroid panel (TSH, T3, T4, and free T4) will also be collected at Visit 1.

Qualitative urinalysis will include pH, specific gravity, glucose, ketones, protein, blood, leukocyte esterase, urobilinogen, nitrites, and reflex microscopy.

Abnormal clinical laboratory tests at screening may be repeated, on a case by case basis, after consultation with the Medical Monitor.

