6.2.12 Unscheduled Visits

Unscheduled visits will be handled in an identical manner to early withdrawal assessments. If this results in multiple records for a given visit, then the scheduled visit will take highest precedence, followed by early withdrawal visits, and unscheduled visits last.

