6.12.2 Laboratory Data

Descriptive statistics for the observed values and change from baseline will be presented by treatment group and visit for each hematology, urinalysis, and serum chemistry (including triglycerides and thyroid panel) parameter. Each continuous measurement will be classified as below, within, or above normal range, based on ranges supplied by the laboratory used. Categorical parameters may also be classified as normal or abnormal based on normal ranges, and subject counts within each category will be summarized. Shift tables in relation to the normal range from baseline to each post-baseline visit will be presented.

Summaries and listings will be presented using the original unit for each parameter as received from the analytical laboratory.

A listing of out of normal range laboratory values throughout the study will be presented. All laboratory assessments, including urine pregnancy tests, drug tests, and serology will also be listed.

A separate listing will be provided for all Alanine Aminotransferase (ALT), Aspartate Aminotransferase (AST), and Bilirubin results at all timepoints for any subjects who meet the criteria for liver function abnormalities as defined in Section 0.

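### Exit and unscheduled values displaced by a scheduled visit reach no by-arm numeric safety summary; worst-post-baseline tables would recover them

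*SAP*

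**What the plan says.** Subjects who stop early are still measured in full. A note to the schedule of procedures in Protocol 6.1 states: "Subjects who prematurely discontinue randomized treatment will have Week 12 procedures performed". SAP 6.2.11 then assigns each ET assessment to the closest visit by midpoints. Its PGI-C example is "windowed with Day 2 to Day 42 as Week 4, Day 43 to Day 70 as Week 8", with Day 71 onward going to Week 12. The same windows serve vital signs, laboratory samples, ECG, FIQR and PROMIS; S-STS has an extra Week 2 window ending on Day 21. If the assigned visit already has a scheduled value, "the scheduled assessment will take precedence, and the early withdrawal assessment will be disregarded (and listed only". SAP 6.2.12 adds "Unscheduled visits will be handled in an identical manner to early withdrawal assessments" and ranks unscheduled values last.

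The by-arm laboratory outputs in SAP 6.12.2 follow the visits: "Descriptive statistics for the observed values and change from baseline will be presented by treatment group and visit", and "Shift tables in relation to the normal range from baseline to each post-baseline visit will be presented". Vital signs (6.12.3), ECG (6.12.4) and the S-STS total score (6.12.5) are also tabulated visit by visit. The output list in SAP section 11 has no by-arm table of worst, last or any-time post-baseline value. Individual data remain: "A listing of out of normal range laboratory values throughout the study will be presented". There is also a listing of ALT, AST and bilirubin at all time points for subjects who meet the liver criteria of SAP 6.2.25.

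**The concern.** Safety and tolerability is a primary objective (Protocol 5.1, SAP 2.1), and Protocol section 4 names raised ALT among the most common treatment-emergent events so far. The exit visit, or an unscheduled visit called for a safety question, is where an unusual laboratory, ECG, vital-sign or S-STS value may be recorded. Under this rule such a value can be collected and listed without entering any numeric comparison between arms. A reader of the report would have to rebuild that comparison from listings.

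The rule also touches secondary efficacy. FIQR, PROMIS and PGI-C are analysed by MMRM (SAP 6.11.4.1 and 6.11.4.4 to 6.11.4.7). The SAP addendum ties baseline-carried-forward imputation to the primary analysis, and the pattern-mixture and tipping-point analyses in SAP 6.11.3 concern the primary endpoint. A subject seen on Day 28 who leaves on Day 40 therefore contributes the Day 28 score. The Day 40 score is omitted, and Weeks 8 and 12 are handled as missing at random.

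**Working it through.** **Windows.** Protocol Table 3 gives Week 2 as Day 14 ± 2, Week 4 as Day 28 ± 4, Week 8 as Day 56 ± 4 and Week 12 as Day 84 ± 4. The midpoints are (14 + 28)/2 = 21, (28 + 56)/2 = 42 and (56 + 84)/2 = 70. These reproduce the SAP boundaries.

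**Displaced ET days.** An ET value is displaced when it falls after a completed scheduled visit but still inside that visit's window. Possible ET days run from Day 2 to Day 83, which is 82 days.

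| Visits 4 and 5 on | Displaced days | Count | Share of 82 |
|---|---|---|---|
| Days 28 and 56 (on time) | 29-42, 57-70 | 14 + 14 = 28 | 34% |
| Days 32 and 60 (both 4 days late) | 33-42, 61-70 | 10 + 10 = 20 | 24% |
| Days 24 and 52 (both 4 days early) | 25-42, 53-70 | 18 + 18 = 36 | 44% |

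For S-STS with visits on time, Days 15-21 are added: 28 + 7 = 35 of 82 (43%). Taking Days 28 and 56 out of the denominator changes 28/82 to 28/80 (35%).

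**From days to subjects.** The documents give no withdrawal rate; the 15% in SAP section 4 is exclusion from the efficacy population. Assume that 10% to 30% of the 100 subjects per arm withdraw, with exit days spread evenly. Then between 100 × 0.10 × 0.24 = 2.4 and 100 × 0.30 × 0.44 = 13.2 subjects per arm have displaced exit values. If exits come early (assumed hazard halving every 28 days), the displaced share of exits is 27% with on-time visits, and 18% or 36% with both visits late or early.

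**Unscheduled values.** In a subject who attends Weeks 4, 8 and 12 on time, the other days from Day 2 to Day 88 number 87 − 3 = 84. All 84 map to a window with a scheduled value, so no unscheduled value enters a by-visit table.

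**Which efficacy analyses are touched.**
- Pain NRS, DSIS and rescue use have their own diary windowing (SAP 6.2.17.2, 6.2.18, 6.2.19), with the last diary day as anchor after withdrawal. Not affected.
- The Week 12 NRS responder result comes from the diary, with missing counted as non-response (6.2.17.3). In the Week 12 PGI-C responder analysis, a subject with a displaced exit score has no Week 12 value and counts as a non-responder (6.2.20). Neither is affected.
- The FIQR, PROMIS and PGI-C MMRMs omit the displaced scores.

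**Illustrative size for FIQR.** By SAP 6.2.21 the total runs from 0 to 90/3 + 20 + 100/2 = 100. Let a and p be the numbers of displaced exits on drug and placebo. Let D be the points by which an exit score is worse than the value the model implies, and take n = 85 per arm (SAP section 4). A rough shift in the between-arm difference at the visit concerned is D(a − p)/n. The values of a, p and D are assumptions.
- a = p: shift 0.
- a = 8, p = 4, D = 10: 10 × 4/85 = 0.47 points, flattering the drug.
- a = 4, p = 8, D = 10: 0.47 points the other way.
- a = 10, p = 3, D = 20: 20 × 7/85 = 1.65 points, flattering the drug.

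For scale, with an assumed SD of 18 and baseline correlation of 0.7, the standard error is 18 × √(1 − 0.7²) × √(2/85) = 1.97. The shifts of 0.47 and 1.65 are then 0.24 and 0.84 standard errors.

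**The case against.** Much of the case for the plan stands. AE tables are by treatment group (SAP 6.12.1), and the protocol routes many of these events into them. A laboratory abnormality that needs intervention, or leads to interruption or discontinuation of drug, is an AE (9.4.1). Clinically significant ECG deterioration is summarised as a TEAE (12.7.3), and suicidality after baseline is an AE (9.3.6). A reader might infer that a subject who leaves because of a laboratory or ECG finding vanishes from the comparison of arms. The documents do not support that. The uncovered part is the numeric extreme that is not an AE, since 9.4.1 leaves out laboratory abnormalities without symptoms, intervention or an effect on dosing.

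A reader might also infer that required retests are a major loss, because Protocol 9.3.5 says "Possibly drug-related or clinically significant abnormal values of uncertain causality must be repeated". Mostly it works the other way. When the abnormal result came from a scheduled visit, that result keeps its place in the shift table and the retest is set aside. Only a retest that is worse within the same category is lost, and categories of below, within and above normal could not show it anyway.

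The most tempting reading is that displaced records are selected for bad outcome and so tilt FIQR and PROMIS toward the drug. The rule covers every withdrawal reason in Protocol 7.4, including withdrawn consent, noncompliance, sponsor termination and COVID-19. Unscheduled visits may be for retraining (10.3.1). No withdrawal rate by arm is given. Protocol 6.3 reports no AE difference from placebo in the two previous Phase 2 studies, and lack-of-efficacy exits could be commoner on placebo, which would reverse the sign.

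Finally, closest-visit mapping is a coherent prespecified rule. The addendum was written after database lock and unblinding, so changing the main models now would be a data-aware change. That also stands.

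**Conclusion.** The point holds for the numeric safety summaries. When a scheduled value fills the window, ET and unscheduled laboratory, vital-sign, ECG and S-STS values leave every by-arm table of those measures, and no planned output brings them back. The reach is 34% of possible ET days with on-time visits (24% to 44% with both visits 4 days late or early), and every unscheduled value in a subject with all scheduled visits. ET values that land in an empty window are kept, so this is not a loss of all exit data. The number of subjects depends on a withdrawal rate that the documents do not give.

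For efficacy the point is narrower. Only the FIQR, PROMIS and PGI-C MMRMs omit displaced scores. Bias between arms arises only if deterioration-related dropout differs by arm; under the assumptions shown it is a fraction of a standard error and can take either sign. No power or alpha figure changes.

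**What to change.** In SAP 6.12.2 to 6.12.5, add by-arm tables of the worst post-baseline value over all scheduled, ET and unscheduled results:
- Labs, ECG and vital signs: shift from baseline to worst value, with highest and lowest shown separately where both directions matter.
- ALT, AST and bilirubin: worst value by multiples of ULN; the multiples already named in SAP 6.2.25 and Protocol section 11 can serve as cut points.
- S-STS: maximum total score.

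Keep the closest-visit rule for the main FIQR, PROMIS and PGI-C MMRMs. Add one sensitivity analysis in which a displaced ET score goes to the next scheduled visit not yet reached (with on-time visits, Days 29-42 to Week 8 and Days 57-70 to Week 12). Leave the PGI-C responder rule unchanged.

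The cost is a few extra tables and one model run per score, with no new data. Worst-value tables favour subjects with fewer measurements, so the number of assessments per arm should be shown beside them. With on-time visits a forward-mapped score can be 56 − 29 = 27 days before its nominal visit; the present rule already accepts 28 − 2 = 26. If the preceding visit was 4 days early, the gap can reach 56 − 25 = 31 days. SAP section 6 allows additional justified tables in the clinical study report. Anything added after unblinding should be labelled post hoc.
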